1. INTRODUCTION

1.1. Background

In previous clinical studies of eltrombopag in ITP, there are some patients who have been reported as non-responders at the maximal approved dose of 75mg daily. The trend in both normal volunteers (Jenkins et al Blood 2007) and in patients with ITP suggests an increasing response rate with increasing doses of eltrombopag up to a dose of 75 mg . ([name] et al. NEJM 2007) In fact, at 50 mg there was a 70% response rate and at 75 mg there was an 81% response rate in the initial ITP study.([name] et al. NEJM 2007) Furthermore, the occurrence of platelet counts $> 200,000/\mu\text{l}$ was substantially more frequent at 75 mg compared to 50 mg as well. In the confirmatory study, approximately 1/3 of the patients who did not respond to 50 mg did subsequently respond to 75 mg, although the response rate overall was only 59% compared to 16% in placebo.([name] et al. Lancet 2009). In the RAISE study, two key issues emerged. First the majority of patients ended up on 75 mg by the end of the study. Second, the odds of responding at each assessment point was barely 50% if not very occasionally below 50% during the study. (Cheng et al. Lancet 2011) Altogether these data suggest to us that a higher dose of eltrombopag may be useful in some patients

Data from the PETIT and PETIT2 studies in pediatric patients (who seem to metabolize eltrombopag differently especially at younger ages) found that in the middle and lowest age cohorts, even doses of 75 mg were sometimes insufficient to obtain a response. This was confirmed in the youngest cohort who thus far have required doses $> 2 \text{ mg/kg}$ in almost all cases (and even $> 3 \text{ mg/kg}$) in order for the children to respond. In the middle cohort this was dose limiting because a ceiling of 75 mg was reached rapidly if the child weighed more than 37.5 kg. ([name] et al, PETIT in press Lancet Haem 2015)

Additional data accumulating from the pediatric clinical trials support this observation that younger children require an increased weight base dose to reach a platelet response. In the PETIT Study, the older pediatric patients (12-17 year olds) average dose was 1.2 mg/kg compared with 2.9 mg/kg to the youngest cohort (1-5 year olds) ([name] et al, in press Lancet Haem 2015). The PETIT II study also reported an increased proportional dose requirement in the youngest cohort. (Grainger, in press Lancet Haem 2015). All of the available data using eltrombopag in research trials or clinical practice in > 170 children have not identified any new safety concerns and the side effect profile remains favorable, particularly given the alternatives in this age group. (Ramaswamy et al, JPeds, 2014)

Published data has shown pharmacokinetics, safety and tolerability of eltrombopag in healthy volunteers at an escalated dose range 100-200mg po daily for 5 days. (Matthys et al J Clin Pharmacol. 2011). Healthy volunteer data also showed a dose dependent platelet response, with a safety profile similar to placebo. Data recently presented at the ASH 2011 Meeting in refractory severe aplastic anemia patients showed safe dose escalation of eltrombopag to a maximum of 150mg with a 44% response rate. (Olnes et al. NEJM 2013) Additional phase I data presented in stem cell transplant patients, has shown doses of up to 300 mg daily have not caused dose limiting toxicities and are also well tolerated (Liesveld et al. Blood 2011).

Altogether these data suggest both that a higher dose in ITP may be more efficacious in increasing the platelet count. Furthermore the same data also suggests there is no overt increase in toxicity in normal volunteers, oncology patients or aplastic anemia patients treated with doses as high or higher than those proposed in this study.

1.2. Rationale

It therefore seems possible, even likely, that in ITP patients who did not respond at a dose of 75mg daily, eltrombopag could be more effective at a higher dose. Therefore, we would like to explore doses as high as 150 mg po daily in order to see if we can demonstrate efficacy in those patients unresponsive to 75 mg daily. We propose a double blind randomized controlled trial in ITP patients who have been defined as 'non-responders' at the maximum dose (75mg) of eltrombopag. The study will also assess efficacy and toxicity at higher daily doses (100mg, 125mg, 150mg) in this population. The study will be performed at a single center in North America, (Weill Cornell Medical College). There will be two parts to it. First the randomized double blind part to be described next. Subsequently an open label study similar to the EXTEND study (TRA105325;<https://www.clinicaltrials.gov/ct2/show/NCT01880047?term=[name]+Dose+Escalation&rank=1>) in patients who responded at doses of 100 to 150mg to see if they maintain or even improve their response and to investigate the eltrombopag safety profile over up to 18 months at these higher doses.

Furthermore, the patients randomized to the placebo arm can go on open label treatment at higher doses if they did not increase their counts on placebo. Even though open label, they will serve as a confirmatory group.

2. OBJECTIVE(S)

2.1. Primary Objective

To determine the proportion of patients with chronic ITP who do not respond to 75 mg of eltrombopag daily given for at least 3 weeks but then do respond to eltrombopag given daily first for 2 weeks at doses of 100, then for 2 weeks at 125 mg and finally for 4 weeks at a dose of 150mg daily. The intial double-blind phase will stop if/when the platelet count exceeds 100,000/uL. Complete response (CR) will be defined as 2 consecutive platelet counts of greater than or equal to 50,000 AND an increase of greater than or equal to 20,000 from the study baseline within the 8 week increased dose window not as a result of rescue treatment. Partial response (PR) will be defined as 2 consecutive platelet counts of greater than or equal to 50,000 OR an increase of greater than or equal to 20,000 from the study baseline within the 8 week increased dose window not as a result of rescue treatment.

2.2. Secondary Objectives

To determine efficacy of administration of increased dosage of eltrombopag to subjects with chronic ITP who did not respond to current maximally approved daily dose of 75 mg for at least 3 weeks by measuring: number of weeks of platelet counts of response; number of patients achieving a platelet count $> 100,000$, and number of platelet counts per patient $> 100,000$. (Note if a platelet count $> 100,000$ is achieved that week and the subsequent weeks of the 8 week study will be considered to all be over 100,000 for purposes of all analyses).

To determine efficacy of administration of increased dosage of eltrombopag to subjects with ITP who did not respond to current maximally approved daily dose of 75 mg for at least 3 weeks by measuring HRQoL and bleeding scores.

To determine the safety of administration of increased dosage of eltrombopag to subjects with ITP who did not respond to current maximally approved daily dose of 75 mg for at least 3 weeks.

To evaluate if there are subgroups of patients (despite this endpoint being underpowered) who are more likely or less likely to either respond or to experience adverse events based on:

[figure not shown]
Starting platelet counts, splenectomy status, concomitant meds e.g, daily prednisone at a maximum dose of 20mg daily, duration of ITP since diagnosis, starting Hemoglobin, WBC, and Absolute Neutrophil Count (ANC), starting ALTs, bilirubins or Alk Phos levels, Platelet Reticulocyte Count.

3. INVESTIGATIONAL PLAN

3.1. Study Design

Double-blind, randomized, placebo-controlled trial in subjects with ITP who are 'non-responders' at the maximum package insert dose (75mg) of eltrombopag; non-responders are those with platelet counts $< 50,000$ despite taking 75 mg/day of eltrombopag for at least 3 weeks.

Study Design (First part): 8 Weeks

Informed consent and assent of minors will be obtained by the principal investigators or sub-investigators. Typically, informed consent/minor assent will be obtained in the outpatient clinic, although inpatients may have this discussed with them as well. Consent will be obtained after review of clinical information and satisfaction of eligibility criteria. Subjects will be randomly allocated at a two to one ratio to receive active treatment or placebo. All subjects must be ≥ 3 years old and able to swallow a tablet. in the study will receive 75 mg eltrombopag and then be randomized to receive either an additional 25 mg of eltrombopag or matching placebo tablet dispensed by the research pharmacy

Subjects and investigators will be blinded to randomization. Randomization will be stratified according to splenectomy status. Randomization will be performed at the time of informed consent with a computer generated randomization table as per the pharmacy. Subjects may enroll and begin taking 75 mg eltrombopag for at least 3 weeks. When subject's platelet count is $< 50,000$, the subject may begin day 1 of the study. Subjects and investigators will be blinded to assignment and treatment in this phase. Eltrombopag will be administered for 8 weeks or until the platelet count exceeds 100,000; at this point dosing will stop, subject will be considered a responder and the subject will eligible for entering Part 2 (the long term treatment part of the study) if desired and agreed to be appropriate by the subject giving consent, and the treating physician. The dose at which the subject achieved the primary endpoint ($> 50,000$ and increase by $> 20,000$) will be considered the dose of response. Even if a patient achieves a response, if the platelet counts remains $< 100,000$, then the dose escalation schema in the figure above will continue.

[figure not shown]
Dose escalation will continue, despite satisfaction of the primary endpoint of study ($> 50,000$ and $> 20,000$ above baseline), until the platelet count reaches 100,000. The rationale for this approach is to maximize clinically relevant responses for the subjects and standardize data for analysis. Subjects will stop study medication if the platelet count is within the normal range, thereby minimizing any safety risk associated with elevated platelet count. By continuing to dose escalate subjects until the platelet count is $> 100,000$, the maximum response and correlation of dose will be tracked allowing better understanding of sustained response and dose-dependent response, which can be applied to future consideration dosage for periods of short-term hemostasis (i.e surgical procedures). The 8 weeks of data collected in enrolled subjects on the standardized

protocol will have the balance of consistency of dosage and unequivocality of response while maintaining subject safety.

If agreed on by the P-I, subjects may obtain local counts or see their local hematologist for study visits. All study-required procedures will be faxed to the P-I for review. The appropriate dosing adjustments will be determined by the P-I.

According to the new consensus guidelines (Provan Blood, 2009), male and female subjects with > 1 year duration of ITP are diagnosed with chronic ITP. Enrollment began with adult subjects \geq 18 years of age, and was extended to include pediatric patients $>$ 12 years of age after a review of this unblinded safety information by the independent Data Safety Monitoring Officer (DSMO). Additionally, we will now allow the inclusion of pediatric patients \geq 3 year of age to enroll on the protocol. The rationale for treating patients on this study is to allow people to be successfully treated and thus increase their platelet count by using a higher dose of eltrombopag when they do not respond to 75 mg daily of eltrombopag. Since some children do not respond to 75mg, the rationale and the dosing (when and how to increase) would be the same.

Long Term Treatment Extension (Part 2): (48 months)

After 8 weeks or once dosing is stopped because the platelet count is $>100,000$, the subject will be unblinded, once the data forms are complete with the assistance of the research pharmacy.

Subjects who received and responded to eltrombopag higher dose treatment will have the option to continue therapy with periodic monitoring and ongoing dose adjustment on the open-label extension study.

Subject who had a platelet count $> 100,000$ can enter Part 2 at the dose at which the subject met primary response criteria after the platelet count decreases to $< 100,000$ /uL on serial monitoring in the immediate post-study monitoring period.

Subjects randomized to the placebo group who did not respond will have the opportunity to receive open label escalated dose eltrombopag over 8 weeks following the study protocol as if they had been randomized to active drug in the study. This group will provide the “confirmatory group” to see if the rate of response in the randomized group can be confirmed in this group.

Consent will be obtained for additional monitoring with bone marrow aspirate and biopsy at 1 year (at year 2, year 3, year 4) and additional ophthalmologic examinations for cataracts at 6 months and 18 months.

It is considered standard of care to monitor all patients as possible who have been on eltrombopag treatment for 1 year because of the higher doses of eltrombopag administered in this protocol. All subjects will have bone marrow aspiration/biopsies for their clinical care, no bone marrows will be performed for research purposes only.

Optional PK sampling will be done 4 weeks after the subject has been on active study drug (or at another time point if this is not convenient). There will be 3 samples drawn: the 1st sample will be drawn prior to taking the study drug for that day, the 2nd PK sample will be drawn 2-4 hours after the dose was taken and the 3rd sample will be drawn 5-8 hours after the dose was taken. These PK tests are being done to measure how much eltrombopag is in the blood at various time points following administration of eltrombopag and can be compared to published data.

The trial will have an 80% statistical power at the 5% level of significance (two sided) to detect a difference in the proportion of subjects receiving increased dose of eltrombopag with a primary response (2 consecutive platelet counts of > 50,000 and an increase of > 20,000 from the study baseline with in the 8 week increased dose window not as a result of rescue treatment) to subjects without a primary response in the placebo group assuming 50% of subjects randomized to active drug will have a response and 5% of subjects randomized to placebo would have a response. The same statistical test will be run for subjects who achieve partial response. An interim analysis was performed after 18 subjects to test for futility and efficacy.

Dose modification during the long term extension portion of the trial will be made on the basis of individual platelet response to a maximal dose of 150mg. All subjects can be monitored at 4 weeks intervals and then can go to every 8 weeks for the remainder of the study at the discretion of the investigator (investigator may require subjects to come in for additional monitoring if deemed necessary).

If the platelet count is > 150,000 ul and < 400,000 ul the daily dose will be adjusted and if > 400,000 ul the medication will be held and monitor will be as per the prescribing information for eltrombopag in the package insert. However, if the P-I determines that adjusting the subject's dose will negatively affect the subject, he or

she may decide not to escalate or reduce the subject's dose. Circumstances in which this may occur include, but are not limited to: investigator is tapering other medications or the subject has a viral infection. Viral infections have been known to both increase and decrease platelet count in patients with ITP. It is suggested that the increased presence of inflammatory molecules during a viral infection increases platelet production, causing platelet count to increase. Alternatively, platelet count may decrease by virtue of activating the reticuloendothelial system causing greater phagocytosis of antibody-coated platelets and/or platelet production.

Laboratory/Assessment Testing

Please see Appendix 1 for Schedule of Events.

Screening

CBC with Differential
Reticulocyte Count
Peripheral Smear
CMP (Sodium, Potassium, Bicarbonate, Chloride, BUN, Creatinine, Glucose, Calcium, Total Protein, Albumin, including AST/ALT, Fractionated Bilirubin Level)
Urine Pregnancy Test (when appropriate)

At Enrollment: (Part 1)

CBC with Differential
Reticulocyte Count
Peripheral Smear
CMP (Sodium, Potassium, Bicarbonate, Chloride, BUN, Creatinine, Glucose, Calcium, Total Protein, Albumin, including AST/ALT, Fractionated Bilirubin Level)
Platelet Reticulocyte Count
Eye Examination for caratacts
History, Physical with Vital Signs and Bleeding Score
HRQOL

Every 2 Weeks until week 8:

Reticulocyte count, Platelet Reticulocyte count
Peripheral Smear (if indicated)
CMP
History, Physical with Vital Signs and Bleeding Score

Long Term Treatment Extension: (Part 2)

Performed at each study visit:

CBC with Differential platelet count, Reticulocyte count, Platelet Reticulocyte count
Peripheral Smear (if indicated)
History, Physical with Vital Signs

After the end of treatment during the dose escalation phase, all subjects can be monitored at 4 weeks intervals and then can go to every 8 weeks for the remainder of the study at the discretion of the investigator (investigator may require subjects to come in for additional monitoring if deemed necessary).

After 6 months on therapy:

Eye Examination

After 12 months on therapy:

Bone Marrow Aspirate and Biopsy
HRQOL

After 18 months on therapy:

Eye Examination

After 24 months on therapy

Bone Marrow Aspirate and Biopsy

*Please Note: A bone marrow aspiration/biopsy will only be performed at 24 months if the subject's reticulin fibrosis grade is a 2 or 3 during the 12 month procedure.
HRQOL

After 36 Months on therapy

Bone Marrow Aspirate and Biopsy

*Please Note: A bone marrow aspiration/biopsy will only be performed at 36 months if the subject's reticulin fibrosis grade is a 2 or 3 during the 24 month procedure.

HRQOL

After 48 Months on therapy

Bone Marrow Aspirate and Biopsy

*Please Note: A bone marrow aspiration/biopsy will only be performed at 48 months if the subject's reticulin fibrosis grade is a 2 or 3 during the 36 month procedure.

HRQOL

Post Study Period after completion of dosing

Weekly

CBC with Differential platelet count, Reticulocyte count, Platelet Reticulocyte count
Peripheral Smear (if indicated)

History, Physical with Vital Signs and Bleeding Score
HRQOL (Week 1 – End of 8 Week Blinded study/ End of Extension Study)

Every 2 Weeks until week 4:
CMP
History, Physical with Vital Signs and Bleeding Score

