4. SUBJECT SELECTION AND WITHDRAWAL CRITERIA

4.1. Number of Subjects:

60 subjects will be enrolled.

4.2. Inclusion Criteria:

Subject or their parent/ guardian has signed and dated a written informed consent

Males and Females aged 3 year or older, who can swallow a tablet, and are diagnosed with chronic ITP according to the new consensus guidelines (Provan, Blood, 2009) are eligible.

No indication of a disease which may cause thrombocytopenia other than ITP---- no specific testing required

Subjects with thrombocytopenia $\leq 50,000 /uL$ after at least 21 days of daily dosage with eltrombopag 75mg

Stable dosage of concomitant treatments for ITP
 ≥ 2 weeks or longer (corticosteroids);

At least 2 weeks from rescue therapy for ITP (WinRho, IVIG, corticosteroids, platelet transfusion) or 1 week if therapy has clearly been ineffective

At least 4 weeks from rituximab treatment

Pregnant or Lactating Women are excluded

Women of child-bearing age with a negative pregnancy test within 7 days of enrollment and who agree to use acceptable methods of birth control will be eligible for this study

Female subjects or female partners of male subjects must either be of non-child bearing potential (hysterectomy, bilateral oophorectomy , bilateral tubal ligation or post menopausal for more than one year) OR, if of child bearing potential, using one of the following highly effective methods of contraception.
-complete abstinence from intercourse

- Intrauterine device (IUD)
- Two forms of barrier contraception. diaphragm plus spermicide, or for males condoms plus spermicide.
- Male partner is sterile and is the only partner of the female.
- Systemic contraceptives

4.3. Exclusion Criteria:

Previous history of eltrombopag-related LFT elevation that required sustained interruption of treatment

Previous history of immediate or delayed hypersensitivity reaction or idiosyncrasy to drugs chemically related to eltrombopag

Known HIV Infection

History of Arterial or Venous Thrombosis within the past year or requiring ongoing therapy

Known Active Hepatitis C infection

Elevated AST/ALT or Creatinine > 1.5 times upper limit of normal in 4 weeks prior to enrollment*

Abnormalities in WBC, ANC and Hemoglobin > 1.5 times upper or lower limit of normal*

* Subjects can be rescreened to be included

4.4. Withdrawal Criteria:

Subject may withdraw consent at any time

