5. STUDY TREATMENTS

5.1. Treatment Assignment

Subjects will be randomly allocated in a two to one ratio to receive treatment or placebo. Subjects and investigators will be blinded to randomization. Randomization will be stratified according to splenectomy status. Randomization will be performed at the time of informed consent with a computer generated randomization table

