- Must return weekly for repeat liver chemistries (ALT, AST, alkaline phosphatase, bilirubin) until they resolve, stabilize or return to within baseline values
- If at any time the subject meets any of the liver chemistry stopping criteria 1 – 5, proceed as described above
- If, after 4 weeks of monitoring, ALT <3x ULN and bilirubin <2x ULN, monitor subjects twice monthly until liver chemistries normalize or return to within baseline values.

Protocol Stopping Rules

Novartis and the Principle Investigator may terminate the study at any time. Early termination may occur due to emergent risk information or the decision by Novartis to discontinue the development of Eltrombopag.

Dose Escalation Rules

In Part 1 of the study, subjects will be randomly allocated at a two to one ratio to receive active treatment or placebo. All subjects in the study will receive 75 mg eltrombopag and then be randomized to receive either an additional 25 mg of eltrombopag or matching placebo tablet dispensed by the research pharmacy.

Eltrombopag will be administered bi-weekly for 8 weeks. If platelet count does not exceed 100,000, the additional eltrombopag or matching placebo tablet will be increased by 25 mg until the patient receives 75 mg eltrombopag and 75 mg eltrombopag or matching placebo (100mg x 2 weeks, 125 mg x 2 weeks, 150 x 4 weeks). If the patient's platelet count exceeds 100,000 during part 1 dosing will stop, subject will be considered a responder, and the subject will eligible for entering Part 2 (the long term treatment part of the study).

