10. APPENDICES

10.1. Appendix 1

Attached Table 1: Study Assessments and Procedures

| Part 1 | Screen < 28 days | Day 1 | Week 2 | Week 4 | Week 6 | Week 8 |
|-------------------------------------------|------------------|-------|--------|--------|--------|--------|
| Written Informed Consent | X | | | | | |
| Inclusion/Exclusion Criteria | X | | | | | |
| Demographics | X | | | | | |
| Register | X | | | | | |
| Eye Exam | X | | | | | |
| Pregnancy Test * | X | | | | | |
| Randomization | X | | | | | |
| History and Physical (Vital Signs) | | X | X | X | X | X |
| Bleeding Score | | X | X | X | X | X |
| HRQOL | | X | | | | |
| CBC | X | X | X | X | X | X |
| Reticulocyte | X | X | X | X | X | X |
| Platelet Reticulocyte | X | X | X | X | X | X |
| Peripheral Smear* | X | X | X | X | X | X |
| CMP | X | X | X | X | X | X |

| Part 2 | 6 Month | 12 Month | 18 Month | 24 Month | 30 Month | 36 Month | 42 Month | 48 Month |
|--------------------------------|---------|----------|----------|----------|----------|----------|----------|----------|
| Eye Exam | X | | X | | | | | |
| Bone Marrow Examination | | X | | X** | | X** | | X** |
| HRQOL | | X | | X | | X | | X |
| CBC | | | | | | | | |
| Reticulocyte | | | | | | | | |
| Platelet Reticulocyte | | | | | | | | |
| Peripheral Smear * | | | | | | | | |
| CMP | | | | | | | | |

*If clinically indicated

** Bone marrow aspirations/biopsies will be performed annually depending on the reticulin fibrosis grade of the bone marrow performed at year 1. A bone marrow

aspiration/biopsy will be repeated the next year if the subject's reticulin fibrosis grade is a 2 or 3.

| Post Study Period | Week 1 | Week 2 | Week 3 | Week 4 |
|------------------------------|---------------|---------------|---------------|---------------|
| CBC | X | X | X | X |
| Reticulocyte | X | X | X | X |
| HRQ0L | X | | | |
| Platelet Reticulocyte | X | X | X | X |
| Peripheral Smear * | X | X | X | X |
| CMP | X | | X | |

10.2 Appendix 2

PHARMACOKINETIC SAMPLING

PK Sample Collection

After a minimum of 4 weeks on active study drug, 2mL blood samples for PK analysis will be collected in K2 EDTA-containing tubes. One sample will be collected at each of the following times: within 1 hour prior to eltrombopag dosing (pre-dose sample), and at 2- 4 hours and 5-8 hours after eltrombopag dosing.

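### Allocation is drawn at consent or screening, before the 75 mg run-in and Day 1 platelet gate that 3.1 allows, and the date of the baseline count is not fixed

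*Combined protocol and SAP*

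**What the plan says.** **Timing of allocation.** Section 3.1: "Randomization will be performed at the time of informed consent with a computer generated randomization table as per the pharmacy". Section 5.1 repeats it: "Randomization will be performed at the time of informed consent with a computer generated randomization table". In the Part 1 table of Appendix 1 the only mark for randomisation ("Randomization | X") is in the Screen column; the Day 1 column has none.

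**What may follow allocation.** In 3.1 the next step is: "Subjects may enroll and begin taking 75 mg eltrombopag for at least 3 weeks". Once the count is below 50,000, "the subject may begin day 1 of the study".

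**Text pointing the other way.** Section 3.1 also says: "Consent will be obtained after review of clinical information and satisfaction of eligibility criteria". The inclusion criteria in 4.2 require a low count "after at least 21 days of daily dosage with eltrombopag 75mg". The Dose Escalation Rules say: "All subjects in the study will receive 75 mg eltrombopag and then be randomized to receive either an additional 25 mg of eltrombopag". That last sentence is weaker evidence on sequence, because it may only describe the background dose plus the add-on tablet.

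**Analysis sets.** Efficacy is analysed by intention to treat in everyone randomised (8.3.1). Only the safety set requires at least one dose (8.3.1.2).

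**Baseline.** Sections 2.1 and 3.1 measure the rise of 20,000 from the *study baseline*. Sections 6.3 and 8.3.1.1 measure it from the baseline count *at enrollment*. A CBC is scheduled at both Screen and Day 1.

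**The concern.** The trial asks whether patients who failed 75 mg respond to more. If allocation is drawn at consent and the run-in follows, a subject can hold an allocation for weeks and then rise above the gate or withdraw before taking a blinded add-on tablet. That subject is outside the trial's question but inside the primary analysis. The result is dilution of the treatment difference and some loss of power.

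The run-in is not the only route. A subject who failed 75 mg before consent can still be allocated well ahead of Day 1, since Appendix 1 allows a screening interval of under 28 days and 6.1 allows 30.

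The baseline matters for a related reason. Section 3.1 uses *enroll* for the moment before the run-in. An enrolment baseline could therefore be a count taken before 75 mg was tried, or the count on Day 1. Both CR and PR use the rise from baseline, and 3.1 gives PR the same statistical test.

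**Working it through.** **Inputs.** Response 50% on active and 5% on placebo, two-sided 5%, 80% power (3.1, 8.2.1). Allocation 2:1 (3.1, 5.1). Sample size 36 (8.3.1), now 60 (4.1; 8.2.1 allows expansion to 60). The share r who never start Day 1 is not in the documents; 0, 10% and 20% are my assumptions. I take r as equal in both arms, because the gate precedes any difference in treatment and allocation is blinded.

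**Step 1: reproduce the plan's 36.** The weighted mean rate is (2×0.50 + 0.05)/3 = 0.35. With the pooled-variance formula and no continuity correction, the placebo arm needs

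n = [1.960·√(1.5×0.35×0.65) + 0.842·√(0.50×0.50/2 + 0.05×0.95)]² / 0.45² = 11.03, rounded up to 12.

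That gives 12 + 24 = 36, as in 8.3.1. It contains no allowance for never-starters.

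**Step 2: outcome of a never-starter.** CR and PR both require counts within the 8-week increased-dose window. A never-starter has none and so does not meet the endpoint. The rates become 0.50(1−r) and 0.05(1−r), and the difference becomes 45(1−r) points: 45, 40.5 and 36.

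**Step 3: power**, by full enumeration of the two binomials at 24:12 and 40:20. The sample-size section names no test, so the choice of test is also an assumption.

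| r | Rates | Fisher, N=60 | Pooled z, N=60 | Fisher, N=36 | Pooled z, N=36 |
|---|---|---|---|---|---|
| 0 | 50% v 5% | 97.6% | 98.6% | 81.5% | 86.7% |
| 10% | 45% v 4.5% | 95.2% | 96.8% | 72.4% | 80.4% |
| 20% | 40% v 4% | 91.3% | 93.4% | 61.0% | 71.9% |

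Power falls below 80% at r of about 37% (Fisher) or 40% (pooled z) for N=60, and about 2% or 11% for N=36. Section 8.3.1.1 names logistic regression. A likelihood-ratio test from an unadjusted logistic model gives 91.5%, 87.6% and 82.6% at N=36, but its true size there reaches about 7%, so I do not rely on it.

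**Step 4: baseline.** Take, as an illustration, a subject at 10,000 before the run-in and 45,000 on Day 1, who passes the gate.

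- *CR.* From the earlier count, the rise condition is reached at 10,000 + 20,000 = 30,000, so the 50,000 floor decides. From Day 1 it is reached at 45,000 + 20,000 = 65,000. Two consecutive counts between 50,000 and 65,000 are CR on one baseline and not on the other.
- *PR.* If the count is still 45,000 at weeks 2 and 4, the rise is 35,000 from the earlier count (PR) and 0 from Day 1 (not PR). This can happen in either arm.

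**The case against.** Three objections carry weight.

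*Never-starters may be rare.* If consent follows eligibility, and eligibility includes a low count after 21 days on 75 mg, a consented subject has already failed 75 mg and only a short gap remains. The post-enrolment run-in rests on one permissive sentence. This stands as a reason why r may be near zero. It does not remove the conflict, because that sentence sits in the same section and Appendix 1 also places allocation at Screen.

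*The outcome of a never-starter is not really open.* A reader might infer that, with no explicit scoring sentence, such a subject could be counted as a responder for having risen on 75 mg, with a much larger loss of power. The documents do not support that: the endpoint needs counts inside the increased-dose window. Non-response is the natural default, and the plan only needs to say so.

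*Enrolment may simply mean Day 1.* Section 3.1 lists enrolment tests separately from screening, and Appendix 1 schedules most of them on Day 1, including bleeding score and HRQOL. The eye examination is the exception: Appendix 1 puts it at Screen. The Day 1 reading is plausible, but it conflicts with the use of *enroll* for the time before the run-in. A reader might also infer that PR can already be met on Day 1 itself. That needs unstated readings of the two-consecutive-counts requirement and of when the window opens, so I do not claim it.

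**Conclusion.** The concern holds as a conflict of sequence plus an undefined baseline date. Followed literally, 3.1, 5.1 and Appendix 1 can put subjects who never took a blinded tablet into the primary analysis.

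The expected effect is dilution. A reader might infer bias or a raised false-positive rate, but the gate precedes any treatment difference and allocation is blinded, so neither follows. Nor is the 60-subject trial shown to be underpowered: at r = 20% Fisher power is still 91.3%. The loss would matter at 36 subjects (61.0% at r = 20%).

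These figures rest on an assumed r, equal in both arms, on the plan's 50% and 5%, and on the choice of test. The baseline point does not depend on r, though it matters only where the enrolment and Day 1 counts differ. Severity is low to moderate.

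**What to change.** For future subjects:

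- Draw the allocation on Day 1, once eligibility on 75 mg is confirmed. Consent stays where it is.
- Move the randomisation mark in Appendix 1 to Day 1, and align 3.1, 5.1 and the Dose Escalation Rules.
- Define baseline once, for every response criterion, as the last count on or before Day 1 and before the first blinded dose.

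For subjects already randomised:

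- Keep the all-randomised analysis as primary and state that never-starters count as non-responders.
- Report the number of never-starters by arm.
- Label any analysis restricted to Day 1 starters as supportive and as defined after the 18-subject interim. Subjects are also unblinded individually after Part 1.

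As wording only, reconcile the entry threshold (at or below 50,000 in 4.2, below 50,000 in 3.1) and the screening interval (under 28 days in Appendix 1, 30 days in 6.1).

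The cost is a short amendment and a pharmacy instruction. No visit, test or patient is added, because the Day 1 visit and its CBC already exist. The one practical burden is that counts from local laboratories must reach the pharmacy before allocation.
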